3.2.2 Potential Benefits

The proposed studies do not have direct, short-term subject benefits. Assessment of risks vs. benefits requires some consideration of the potential benefits to society from the studies

HIC 2000030749

proposed. Obesity affects more than a third of the population of the United States and carries an increased risk of cardiometabolic disorders. Given the considerable potential benefit to society, we believe the risk-benefit ratio for participation in the proposed studies is favorable.

HIC 2000030749

4 Study Objectives

4.1 Hypothesis

Our hypothesis is that coordinated multi-organ response (brown and white adipose tissue, muscle, is modulated by the SNS both in the fasting state and after a meal; however, this coordinated response becomes dysfunctional in obesity. Dysfunctional brain regulation of SNS activation to target organs may explain the increased risk of cardiometabolic disorders in obesity.

4.2 Primary Objective

The primary objective of this study is to determine whether sympathetic nervous system (SNS) activity in adipose tissue (WAT and BAT), muscle and brain is altered in individuals with obesity in comparison to individuals with normal weight. Simultaneous multi-organ SNS activation will be obtained with a radiotracer for norepinephrine transporters (NET) for whole-body Positron Emission Tomography (PET) imaging and microneurography (gold standard test for assessment of muscle SNS activity).

4.3 Secondary Objectives (if applicable)

The secondary objectives of this study are: 1) to evaluate whether gender differences affect peripheral SNS in healthy normal weight and obese men and women in adipose tissue (WAT and BAT) and muscle (resting/fasting); 2) To investigate the relationship between peripheral and central SNS activity in obesity, by correlating SNS activity in peripheral tissues (WAT, BAT, and muscle) and brain; and 3) To investigate NET CNS and peripheral SNS activity before and after a high carbohydrate mixed meal in lean and obese men and women.

4.4 Exploratory Objectives (if applicable)

N/A

5 Study Design

5.1 General Design Description

Aim: To measure peripheral SNS in healthy normal weight and obese men and women in adipose tissue (WAT and BAT), deltoid skeletal muscle, and brain NET at fast and after a mixed meal test (MMT).

The goal of this study is to measure in 20 individuals with normal weight (BMI 18-25 kg/m²) and 20 individuals with obesity (BMI 30-50 kg/m²) NET-binding in WAT and BAT to better understand the role of SNS in obesity. SNS activation of a) peripheral tissues: adipose tissue (BAT and WAT) and skeletal muscle; and b) CNS NET will be measured synchronously by using [11C]MIBG whole body

PET imaging in combination with the gold standard measurement of peripheral SNS activity (muscle sympathetic nervous activity (MSNA)). PET and MSNA visits do not need to occur in sequence, i.e. PET scans can occur before or after the MSNA.

Visit 1 - Screening procedures:

HIC 2000030749

Potential subjects will complete pre-screening over the telephone for approximately 10minutes to determine preliminary eligibility based on inclusion/exclusion criteria and basic socio-demographic information will be collected. Potentially qualifying participants will then be screened in person at the Yale New Haven Hospital (YNHH) Research Unit (HRU) or Church Street Research Unit (CSR) with vital signs, EKG, and a medical history and physical exam. A urine pregnancy test will be administered for females.

Oral glucose tolerance test (OGTT) will be administered as follows: Following a 10-hour overnight fast, a nurse will insert an intravenous (IV) catheter. Subsequently, subjects will ingest 7.5 oz of Glucola, which contains 75 g of dextrose in orange flavored water. Blood samples will be taken at -15, 0, 10, 20, 30, 60, 90 and 120 minutes (after glucola ingestion) for the measurement of plasma glucose, insulin, and C-peptide concentrations, and calculation of measurements of insulin sensitivity index (Matsuda Index). Fasting blood obtained from the catheter will be collected for HbA1C, creatinine, liver enzymes (ALT, AST), TSH, hematocrit, and lipid panel. Approximately 40 mL of blood will be drawn at this visit.

Body Composition, Percent Body Fat & Percent Body Water: will be assessed using bioelectrical impedance analysis Tanita® scale (FDA cleared); which is a special multi frequency segmental body composition analyzer that delivers a very mild electrical current through the feet that allows measurement of fat mass, percent body fat, fat free mass, total body water, and percent body water. This test will be performed at screening visit. For better accuracy, measurement of percent fat and percent body water will be obtained with whole body Dual X-Ray Absorptiometry (DXA) scan (Hologic®) (located in the HRU) on screening-OGTT visit. The scanner arm will move over the participant's body from feet to head. The machine uses a small amount of radiation (one tenth of the amount of radiation from a chest x-ray) to measure body fat, muscle and bone density.

Subjects who fail any of the screening procedures will be informed and excluded from participating in the study, however they will be allowed to be re-screened at a later time,

Visit 2 – Whole body PET Imaging Visit - FASTING:

Two weeks after the screening visit, participants who qualified for the study will be asked to come to the PET Center to undergo the whole body [11C]MRB PET scan. Participants will be asked to maintain their regular exercise routine.

Human PET-CT Protocol: [11C]MRB will be synthesized at the Yale PET center based on procedures described and previously performed 1,2. An intravenous bolus dose of MRB (~120mCi) will be injected by an infusion pump. PET data will be acquired dynamically for 120 min using the Siemens mCT-X whole-body PET/CT scanner using continuous bed motion to image perform multiple PET bed acquisitions from the top of the head to the lower abdominal region. A CT scan will be performed for attenuation correction and to help delineate the BAT and other regions of interest (ROIs). Images will be reconstructed with an ordered subset expectation maximization algorithm using point spread function correction and time-of-flight information. To delineate fat (WAT, BAT) and skeletal muscle regions of interests (ROIs),

HIC 2000030749

CT images are first resliced to match the resolution and location of PET images. As performed in previous studies 2, a supraclavicular ROI is first manually drawn on the CT images. Within that area, the fat ROI is segmented using the CT images and an intensity window from -200 to -50 HU. Subsequently the fat ROI is segmented into WAT and BAT ROIs by using the ¹¹C-MRB PET images: Standardized Uptake Value (SUV) ≥ 1.25 for BAT, SUV < 1.25 for WAT.

Brain ROIs for predetermined NET-rich areas of the brain, including the locus ceruleus, raphe, thalamus and hypothalamus were defined in template space and are applied to the PET images by using the participant's MR image as an intermediate step. For analysis of tracer uptake, mean SUV will be reported for segmentation of adipose tissue. Because the distribution volume ratio (DVR) is a more precise measurement of uptake for reversible tracers ³ such as ¹¹C-MRB, regional quantification of ¹¹C-MRB uptake as DVR (V_T / V_{ND}), estimated via multilinear reference tissue model 2 (MRTM2) ^{4,5} ($t^* = 30$ min) using the occipital cortex, a region with low NET density ^{2,5,6} as the reference region. MRTM2 reduces the variability of MRTM (4) parameter estimates by fixing one of the three parameters, the parameter k_2' , which is only related to the reference region time-activity curve, to a common value for all target regions. In this study, the parameter k_2' was fixed to 0.021 min⁻¹, based on previous brain studies and previous BAT PET studies ². In addition to DVR, MRTM2 can estimate R_1 , the relative radioligand delivery, using a 1 tissue compartment model (1TC). For the 1TC model, volume of distribution, $V_T = K_1/k_2$, where K_1 (mL/min⁻¹/mL⁻¹) is the rate constant of radiotracer from plasma to tissue of target organ and k_2 is the rate constant from tissue to plasma. Using a reference region with non-displaceable binding (e.g. occipital lobe) we can estimate similar rate constants: $V_{ND} = K'_1/k'_2$. Recalling that K_1 and K'_1 are the rate constants for transfer from plasma to the tissue and reference region, respectively, then we can estimate relative radioligand delivery as $R_1 = K_1/K'_1$.

The maximum number of attempts for each failed/incomplete imaging and test is 2 times.

Visit 3 – Whole body PET Imaging Visit - High-Carbohydrate Mixed Meal Test (MMT)

High Carbohydrate Mixed meal test (MMT): Two weeks after visit 2, participants will come to the PET Center after a 10-hour overnight fast. A nurse will insert an intravenous (IV) catheter and subjects will ingest a liquid meal (65% CHO, 20% fat, and 15% protein, equal to 40% of daily energy expenditure, per ~16 ounces) to be prepared by the Metabolic Kitchen located at the HRU. Blood samples will be collected at -10, 0, 15, 30, 60, 90, and 120 min for measurement of glucose, insulin and C-peptide concentrations ⁷. Plasma samples will be drawn at baseline and throughout the MMT for measurement of additional hormones (such as leptin, ghrelin, thyroid hormones, and catecholamines) and free fatty acids (FFA) levels. Insulin and glucose will be used to calculate indexes of insulin sensitivity ⁷⁻⁹. Hormones, glucose and FFA will be correlated with PET measurements of brown fat at baseline and during the MMT. Approximately 60 mL of blood will be drawn at this visit.

HIC 2000030749

Participants will undergo whole body [¹¹C]MRB PET scan as described in visit 3. After the MMT, PET data will be acquired dynamically for 120 min using the Siemens mCT-X whole-body PET/CT scanner after an intravenous bolus dose of MRB (~20mCi).

The order of the PET scan visits 2 and 3 will be randomized.

PET and MSNA visits do not need to occur in sequence, i.e. PET scans can occur before or after the MSNA.

Measurement of Energy Intake: Hunger and fullness will be determined immediately before, during and after the PET scans with Visual Analog Scales (VAS).

Visit 4 – Sympathetic Nervous System Activity (SNSA) measurement Visit - Fasting

Two weeks after visit 3, participants will be asked to return for a separated visit for measurements of SNS activity at rest and fasting. This visit will be performed at the Pierce Laboratory ([name] laboratory). The participants will come in the morning (~9am) and will be asked to fast for 10-hour and to maintain their regular exercise routine. The following measurements will be obtained: MSNA, heart rate (HR), blood pressure (BP), electrocardiogram (EKG), and heart rate variability. The proposed procedures will be performed at fasting (baseline). Participants will be asked to maintain their regular exercise routine.

Muscle sympathetic nerve activity (MSNA): Microneurography is the gold standard, most sensitive and reliable MSNA assessment in humans. The primary measure of sympathetic nervous system activity is peripheral nerve activity, as measured by MSNA.

Muscle sympathetic nerve activity will be quantified by identification and measurement of sympathetic bursts in the integrated neurogram and expressed as burst frequency (number of bursts per unit time). ECG surface electrodes are applied to the chest, an elastic band incorporating a strain gauge element is strapped around the thorax for recording respiratory movements, and a sensor cuff of a servopulse-plethysmography arterial pressure monitor (FINAPRES, Ohmeda) is placed on the middle phalanx of the long finger (held at heart level). The experiments are carried out in an environmentally controlled chamber at an ambient temperature of 27.0 ± 0.1 °C. The experiment will begin with a 60-minute control period. During such time the subjects rest in the reclined position.

Measurements of HR, BP, and EKG (beat-to-beat) will also be obtained during the procedure. An intravenous catheter will be inserted into a forearm vein for blood sampling. Following the instrumentation period, resting HR, pulse interval (PI), BP, and MSNA will be recorded for 10 minutes. Following these measurements, plasma will be taken for measurements of insulin, glucose, free fatty acids, norepinephrine, and epinephrine levels. Approximately 20 mL of blood will be drawn at this visit. After the first blood sample and the 10-min rest phase, subjects will begin a seven-minute period of rest with paced breathing (12 breaths per minute) while HR, BP, PI and MSNA are measured. The subjects will synchronize breathing to a metronome set to a cadence of ~12 breaths per minute (0.2 Hz).

Procedure: Microneurography Recording of multiunit postganglionic muscle sympathetic nerve activity (MSNA) will be made from the common peroneal nerve as it winds around the fibular head with the subject in the supine position with the subject's thigh comfortably

HIC 2000030749

supported. This procedure requires us to first trace the course of the nerve using small electrical stimuli applied to the surface of the skin over the nerve or use the ultrasound to visually assist. This allows the microneurographer to find and focus the recording electrode tip on a nerve fascicle associated with muscle sympathetic activity. The time required to focus the electrode on the nerve averages about 30 min and will not exceed 60 min. In optimal conditions the track of the nerve from superficial stimulation is accurate and the nerve remains in position during insertion. An uninsulated subcutaneous electrode will serve as the reference. Mechanoreceptor afferent activity can be recorded during light tapping on the muscle belly or passive muscle stretch. A suitable intrafascicular recording site for MSNA consists of regular bursts and synchronous with the cardiac cycle. The neural activity is amplified (2x104), filtered (0.5-5.0 kHz), rectified, and integrated. The amplified and filtered nerve signal is also led to an audio monitor and through a resistance capacitance circuit (time constant 100 ms). The integrated nerve signal is digitized at 400 Hz along with the ECG signal while respiratory and arterial pressure signals are also sampled at 400 Hz (MacLab 8s). Data for analysis is selected from periods of quiet breathing in which subjects were relaxed and not talking. Microneurography was approved under HIC protocols # 8079, #0512000875, #1609018353 and is currently used under # 2000020950.

Cardiovascular variables. Recorded with a 16-channel computerized data-acquisition system at a sampling Speed of 400 Hz (ADI Instruments PowerLab 9, Castle Hill, Australia). Beat-to-beat DBP, SBP and pulse interval (PI) are determined using peak detection algorithms (44). Brachial artery BP and HR are measured with an automated sphygmomanometer (Colin Medical Instruments Corp, Komaki, Japan). Heart rate and pulse interval will be determined beat-to-beat from lead II of the EKG recording.

[figure not shown]
Visit 5 – Sympathetic Nervous System Activity (SNSA) measurement Visit – Mixed Meal Test (MMT)

Two weeks after visit 4, participants will be asked to return for a separated visit for measurements of SNS activity at rest and after intake of liquid meal. Participants will undergo similar procedures described on visit 4. However, MSNA will be obtained after MMT. The participants will come in the morning (~9am) and will be asked to fast for 10-hour and to maintain their regular exercise routine. A nurse will insert an intravenous (IV) catheter and subjects will ingest a liquid meal (65% CHO, 20% fat, and 15% protein, equal to 40% of daily energy expenditure, per ~16 ounces) to be prepared by the Metabolic Kitchen. Measurements of HR, BP, and EKG (beat-to-beat) will be obtained during the procedure. An intravenous catheter will be inserted into a forearm vein for blood sampling. Following the instrumentation period, resting HR, pulse interval (PI), BP, and MSNA will be recorded for 10 minutes. Following these measurements, plasma will be taken for measurements of insulin, glucose, free fatty acids, norepinephrine, and epinephrine levels. Approximately 40 mL of blood will be drawn at this visit.

HIC 2000030749

Participants will be asked to maintain their regular exercise routine. The order of SNSA Fasting and MMT visits (visits 4 and 5) will be randomized. All study visits will be conducted within an 8-week period (including the two PET and SNSA scans).

Schematic figure of the visits and procedures to be done. The order of the PET scans will be randomized.

Abbreviations: BP=blood pressure, EKG=electrocardiogram, HR=heart rate, MSNA=Muscle sympathetic nerve activity, SNSA=Sympathetic Nervous System Activity

Method of Assignment/Randomization- The order of the PET scan visits 2 (PET-CT Fasting) and 3 (PET/CT-MMT) will be randomly assigned (with a 50% chance of being assigned to each visit). SNSA visits 4 (fasting) and 5 (MMT) will be also be also be randomized (with a 50% chance of being assigned to each visit).

PET and MSNA visits do not need to occur in sequence, i.e. PET scans can occur before or after the MSNA.

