6.4 Statistical Method

6.4.1 Statistical Design

Primary endpoints: Group differences in 1) [¹¹C]MRB-binding in brown adipose tissue (BAT), white adipose tissue (WAT), skeletal muscle, and norepinephrine-rich brain regions (hypothalamus and thalamus); and 2) microneurography (muscle sympathetic nerve activity (MSNA)). Correlations between NET in the brain and peripheral NET and MSNA.

Secondary endpoints: Plasma hormone levels, heart rate, blood pressure, electrocardiogram (beat-to-beat)..

Statistical Analysis: Before statistical testing, all continuous variables will be tested for normality of distribution. Summary statistics will be computed. For between-group comparisons of patient characteristics, two sample t-test or Mann-Whitney U test will be used for continuous variables, and Fisher's exact test for categorical variables. Comparisons of repeatedly measured MSNA will be made using the mixed model analysis. Fixed factors include group and sex and their interactions. Linear contrasts comparing differences between groups or different time points within a group will be estimated.

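### White adipose tissue is a primary endpoint, but the only region described for it is supraclavicular fat below a cut-off on the outcome tracer, so the result speaks for that depot alone

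*Combined protocol and SAP*

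**What the plan says.** The primary objective (4.2) asks whether sympathetic activity in "adipose tissue (WAT and BAT), muscle and brain is altered in individuals with obesity in comparison to individuals with normal weight". It names no fat depot. The primary endpoints in 6.4.1, repeated in the Synopsis and in 5.2, are group differences in binding in "brown adipose tissue (BAT), white adipose tissue (WAT), skeletal muscle, and norepinephrine-rich brain regions (hypothalamus and thalamus"; again no depot is given for white fat.

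The image-analysis text appears three times in near-identical form (Synopsis, 5.1 and 6.3). For fat, "a supraclavicular ROI is first manually drawn on the CT images. Within that area, the fat ROI is segmented using the CT images", using a window of -200 to -50 HU. Then "Subsequently the fat ROI is segmented into WAT and BAT ROIs by using the ¹¹C-MRB PET images": voxels at SUV 1.25 or above are BAT, and the rule for the remainder is "SUV < 1.25 for WAT". Binding is then quantified as DVR with k2' fixed at 0.021 per minute, a value that 5.1 bases on brain and BAT studies.

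No subcutaneous, abdominal or visceral WAT region is described anywhere. The PET acquisition, however, uses "continuous bed motion to image perform multiple PET bed acquisitions from the top of the head to the lower abdominal region".

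**The concern.** The supraclavicular area is where this group looks for brown fat. Calling what is left there WAT raises three problems.

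- **Mixture.** The remainder depends on how much BAT was removed and how much still borders it. Section 2.1.2 reports lower binding in obese women and reads it as a sign of less BAT. On the investigators' own evidence, then, the leftover fat may be a different mix in the two groups being compared.
- **Circular definition.** The region is selected by uptake of the tracer that is also the outcome. No WAT voxel can reach SUV 1.25, and voxels can change class with group or with fasting and fed state.
- **Scope.** Section 2.2 argues that sympathetic activity varies by tissue and builds the hypothesis on regional dysfunction. Neck fat therefore cannot be assumed to represent white fat elsewhere.

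At stake are the WAT part of the primary objective and the WAT-brain correlations of secondary objective 2 (4.3, 6.5.2). Mixed tissue could create a lean-obese difference in the same direction as the BAT pilot, where it might be misread as confirmation. The cap could shrink a true difference.

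**Working it through.** **1. The plan's own figure, and what it covers.** Section 6.4.2 gives BAT DVR of 1.15 (SD 0.19) in lean and 0.80 (SD 0.12) in obese women. The two-sided t-test is taken from its description of the earlier study; alpha is not stated and 0.05 is assumed.

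- Pooled SD = sqrt((0.19² + 0.12²)/2) = sqrt(0.02525) = 0.159
- d = (1.15 - 0.80)/0.159 = 2.20, as stated
- t-test power at d = 2.20: 0.929 with 6 per group, 0.860 with 5, 0.737 with 4

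So 6 per group for 90% and 5 per group for 80% both reproduce. The calculation is for BAT. The documents give no mean, SD or expected difference for WAT in any depot, so power for WAT cannot be computed. What can be given is the smallest standardized difference detectable for any WAT region, with no multiplicity adjustment: d = 0.91 (80% power) or 1.05 (90%) with 20 against 20, and 0.96 or 1.11 with 18 against 18 after 10% loss.

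**2. What the SUV cap can do (hypothetical inputs).** Assume normal voxel SUVs with mean m and SD s. After the cut at 1.25 the mean is m - s·φ(a)/Φ(a), where a = (1.25 - m)/s. Example with s = 0.2:

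- Lean m = 1.25: a = 0, mean after the cut = 1.090, and 50% of fat is classed as WAT
- Obese m = 1.00: a = 1.25, mean after the cut = 0.959, and 89% is classed as WAT
- Difference 0.131 instead of 0.25, so 53% is retained

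Share of the true difference retained, for s from 0.2 to 0.4:

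| Assumed lean v obese mean SUV | Retained |
|---|---|
| 1.40 v 1.10 | 37% |
| 1.25 v 1.00 | 44-53% |
| 1.10 v 0.80 | 56-76% |
| 0.80 v 0.60 | 74-97% |

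The cap matters when much of the fat lies near 1.25 and little when uptake is well below it. The documents contain no voxel data to say which case applies. The cap acts directly on SUV; it reaches DVR only as far as the two move together.

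**3. Why spill-over cannot be sized.** Suppose a fraction f of the lean WAT signal comes from BAT, with f from 10% to 30%, and borrow the pilot's 0.35 as the BAT-WAT contrast. The spurious difference is f × 0.35 = 0.035 to 0.105 DVR. Expressed in SDs:

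- obese BAT SD 0.12: 0.29 to 0.88
- pooled BAT SD 0.159: 0.22 to 0.66
- lean BAT SD 0.19: 0.18 to 0.55
- pooled SD, with f in obese participants half that in lean and the same contrast: 0.11 to 0.33

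The answer moves from 0.11 to 0.88 on choices the documents cannot settle. Moreover, 0.35 is a lean-obese gap in BAT and not a BAT-WAT contrast, f has no source, and none of the SDs is for WAT. None of these figures should be reported as the size of the problem.

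**The case against.** A reader might infer that the trial cannot answer its WAT objective at all. The documents do not support that: the objective names no depot, and a lean-obese comparison of low-uptake supraclavicular fat is possible. The fault lies in what that comparison can be taken to mean.

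A reader might also infer that the sponsor deliberately chose to sample white fat only in the neck. That is not established. The same paragraph announces skeletal-muscle regions, and the aim in 5.1 names the deltoid, yet no muscle steps follow. The text is introduced as earlier practice, and the earlier obesity study imaged only the neck and supraclavicular region (2.1.2). It may be carried-over wording. This stands as an explanation, but not as a defence: a written rule exists, and following it gives the limited result described here.

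The mixing argument is plausible but undocumented. Reconstruction includes point spread function correction, which bears on spill-over. Voxels raised to 1.25 or above are classed as BAT and so leave the WAT region. The pilot also quantified BAT in obese women (DVR 0.80), so their residual fat may border BAT too. These points rule out asserting a bias of any particular size. They do not make the mix equal between groups.

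Finally, abdominal DVR has no pilot data here, and k2' is justified only from brain and BAT. This is a fair reason not to make abdominal fat the sole primary WAT measure.

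**Conclusion.** The point holds as a limit on interpretation. As written, the WAT endpoint describes supraclavicular fat below SUV 1.25. Its composition may vary between groups with adjacent BAT, and its voxel SUV is bounded by construction. It supports no conclusion about subcutaneous or visceral white fat. Neither a difference nor its absence in this region can be read cleanly as a statement about white fat in obesity.

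No magnitude can be given. The direction of net bias is also open, since mixed tissue and the cap can pull in opposite directions. The depot limit rests on the text alone; the mixture argument rests additionally on the investigators' own reading that obese women had less BAT. That the scan contains usable abdominal fat is a fair inference from its stated coverage, not something the documents say, and full abdominal contour at BMI up to 50 is not addressed.

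**What to change.** In 5.1 and 6.3, before images are analysed, pre-specify a WAT region in abdominal subcutaneous fat, drawn on CT alone (-200 to -50 HU, no PET threshold) at one fixed vertebral level in every participant. Take it from the whole-body PET/CT already planned and report it alongside the supraclavicular region.

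Rename the latter 'supraclavicular non-BAT fat' wherever it is an endpoint (Synopsis, 5.2, 6.4.1) and limit its conclusions, including the WAT-brain correlations, to that depot. If the sponsor will not add a region, this renaming and restriction is the minimum.

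Check that k2' fixed at 0.021 per minute is suitable for WAT. Visceral fat is a less safe choice than subcutaneous fat, because it lies near liver, pancreas and kidney, which the rodent data in 2.1.2 list as rich in the transporter.

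Cost: a few sentences, some added image-analysis time, and an abdominal DVR likely to be noisier because counts there are low. No extra scan, radiation, visit or participant is needed.
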